7.0 Protocol Treatment

7.1 Treatment Schedule - Use actual weight (Kg)

Arm	Agent	Dose Level	Frequency	Route
A	Apixaban*	10 mg	Twice daily days 1-7	Oral
		5 mg	Twice daily days 8-180	
B	Dalteparin*	200 IU/kg/day	Once daily for days 1- 30	Subcutaneous Injection**
		150 IU/kg/day	Once daily for days 31-180	

*If a dose of apixaban or dalteparin is not taken at the scheduled time, the dose should be taken as soon as possible on the same day and the prescribed dosing schedule should be resumed. The dose should not be doubled to make up for missed doses.

** The dosage will be calculated on the patient's current weight in kilograms, rounded to the nearest whole kilogram. The syringe dose will be chosen based on the weight adjusted calculation based on the table 7.11. The patient will be taught by on site nursing staff how to administer the medication, and also how to "waste" from each syringe such that the appropriate weight adjusted

dose is delivered.

7.11

Month 1: 200 IU/kg SQ daily

Body Weight (kg)	Dalteparin Dose (IU) once daily
≤ 40	7,500
41-56	10,000
57-68	12,500
69-82	15,000
83-94	18,000
95-107	10,000 & 10,000 = 20,000
108-120	18,000 & 5,000 = 23,000
121-133	15,000 & 10,000 = 25,000
134-147	18,000 & 10,000 = 28,000
148-160	15,000 & 15,000 = 30,000
≥161	200 IU/kg SQ daily

Months 2-6: 150 IU/kg SQ daily

Body Weight (kg)	Dalteparin Dose (IU) once daily
≤ 40	5,000
41-57	7,500
58-77	10,000
78-92	12,500
93-110	15,000
111-130	18,000
131-141	10,000 & 10,000 = 20,000
142-160	18,000 & 5,000 = 23,000
≥161	150 IU/kg SQ daily

- 7.12 **Dalteparin therapy is weight based dosing.** Monthly weights should be performed and communicated with the study coordinator. For patients experiencing more than 10% weight loss or gain, the dose of dalteparin will be adjusted to current body weight. Round according to table 7.11.
- 7.13 Scheduled visits should include a standardized assessment of the signs and symptoms of recurrent thromboembolism, bleeding episodes, and adverse reactions. Patients should be instructed to report to the clinic immediately (or call 911/go to the Emergency Room) if they had any bleeding, or symptoms of recurrent deep-vein thrombosis, pulmonary embolism, or both. Written patient education materials will be provided to each patient outlining signs and symptoms to watch for regarding VTE recurrences (appendix IX). All suspected episodes of recurrent thrombosis should be investigated with the use of objective

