The dalteparin dose should be adjusted for patients experiencing kidney injury. An exclusion criterion for study enrollment is a creatinine clearance <30 ml/min. For those patients already enrolled who then develop worsening kidney function, the dalteparin dose will then be adjusted. For creatinine clearance between 15 and 30 ml/min, the dose of dalteparin should be reduced. During the first month of treatment when the patient is receiving 200IU/kg, the dose will be reduced to 150 IU/kg. During subsequent months, the dose of 150 IU/kg will be reduced to 100 IU/kg. Once the creatinine clearance improves to values > 30 ml/min, the standard dosing will be reintroduced.

For patients with severe kidney injury defined as creatinine clearance < 15 ml/min, dalteparin should be held and the patient should stop the study treatment and receive treatment per the attending physician.

For thrombocytopenia (> 50,000/microliter), no dose adjustment is necessary. For thrombocytopenia (25,000-50,000/microliter), dalteparin dose reduction to 5000 IU/day is necessary. For thrombocytopenia (< 25,000/microliter), dalteparin will be held until platelet count recovers. Once the platelet count improves, the dalteparin dose should be adjusted accordingly.

8.2 **Patients requiring an invasive procedure requiring temporary anticoagulant cessation will be managed as follows:**

- (1) Date and type of procedure will be recorded on the CRF;
- (2) Apixaban will be discontinued at least 48 hours prior to elective surgery or invasive procedures with a moderate or high risk of bleeding, with no drug given on the procedure date; For low bleeding risk procedures, apixaban will be discontinued at least 24 hours. Dalteparin dose will be reduced to 100 IU/kg and given on the morning prior to the procedure date with no drug given on the procedure date;
- (3) Post procedure, the patient could receive prophylactic apixaban (2.5 mg twice daily) or dalteparin (5000 IU once daily) dosing for 48 hours; the first prophylactic dose will be given 24 hours after the procedure;
- (4) Therapeutic apixaban or dalteparin will be withheld until 72 hours after the procedure and not initiated until adequate hemostasis is confirmed.

If apixaban or dalteparin treatment is temporally held, the reason will be recorded on the CRF and the patient can go back on study for up to day 180 of the original treatment schedule.

9.0 **Ancillary Treatment/Supportive Care**

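### Sections 8.1, 8.2 and table 7.11 conflict for some dalteparin patients: above 50 kg the pre-procedure reduction exceeds the low-platelet dose, and at 40 kg or less in months 2-6 the low-platelet dose equals the full table dose

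*Combined protocol and SAP*

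**What the plan says.** Four dalteparin provisions are involved.

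- **Full dose (table 7.11).** The two parts are headed "Month 1: 200 IU/kg SQ daily" and "Months 2-6: 150 IU/kg SQ daily". At 40 kg or less, the listed once-daily dose is 7,500 IU in month 1 and 5,000 IU in months 2-6.
- **Platelet rule (8.1).** "For thrombocytopenia (25,000-50,000/microliter), dalteparin dose reduction to 5000 IU/day is necessary". This is a flat dose with no weight or month term. Below that band the drug is stopped: "For thrombocytopenia (< 25,000/microliter), dalteparin will be held until platelet count recovers". The conflict therefore concerns only the 25,000-50,000 band.
- **Pre-procedure rule (8.2(2)).** "Dalteparin dose will be reduced to 100 IU/kg and given on the morning prior to the procedure date". Nothing is injected on the day itself. The rule covers every patient whose anticoagulant must be interrupted for a procedure. It names no starting dose and does not mention patients already lowered under 8.1.
- **Post-procedure rule (8.2(3) and (4)).** From 24 hours a patient may, optionally, receive "prophylactic apixaban (2.5 mg twice daily) or dalteparin (5000 IU once daily) dosing for 48 hours". Therapeutic dosing is withheld until 72 hours and until hemostasis is confirmed.

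**The concern.** Each rule makes sense for a patient on the full weight-based dose. The difficulty comes when two rules apply to one patient, because one target is flat and the other scales with weight.

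Section 8.1 itself names severe thrombocytopenia as raising bleeding risk on both drugs. A site that follows 8.2(2) literally would give most such patients more dalteparin on the day before a procedure than they were taking. A site that reads the step as applying only when it lowers the dose would not. The text does not choose between these readings, so sites may act differently in an open-label trial whose primary endpoint is major bleeding.

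At low weight the labels stop distinguishing doses. In months 2-6 the full dose, the platelet-reduced dose and the post-procedure prophylactic dose are all 5,000 IU.

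**Working it through.** **Inputs.** Full doses come from table 7.11, the flat 5,000 IU/day from 8.1, and 100 IU/kg from 8.2(2).

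**1. Reproducing the table at 40 kg.** Month 1: 200 × 40 = 8,000 IU, and the nearest listed dose is 7,500. Months 2-6: 150 × 40 = 6,000 IU, and the nearest listed dose is 5,000. Both agree with the table.

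**2. Crossover.** 100 × weight = 5,000 gives weight = 50 kg. The pre-procedure dose is above the platelet dose over 50 kg and below it under 50 kg.

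**3. Doses by weight.** The change is 100 × weight / 5,000 − 1. The cut is 1 − 5,000 / table dose.

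| Weight (kg) | 100 IU/kg (IU) | Change from 5,000 IU | Table dose, month 1 (IU) | Cut to 5,000 IU | Table dose, months 2-6 (IU) | Cut to 5,000 IU |
|---|---|---|---|---|---|---|
| 40 | 4,000 | −20% | 7,500 | 33% | 5,000 | 0% |
| 50 | 5,000 | 0% | 10,000 | 50% | 7,500 | 33% |
| 60 | 6,000 | +20% | 12,500 | 60% | 10,000 | 50% |
| 75 | 7,500 | +50% | 15,000 | 67% | 10,000 | 50% |
| 90 | 9,000 | +80% | 18,000 | 72% | 12,500 | 60% |

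Measured from the full table dose, 100 IU/kg is a true reduction at every whole-kilogram weight from 30 to 160 kg in both periods. The conflict appears only once the platelet rule is already in force.

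**4. Rounding.** Table 7.11 has no 100 IU/kg column, so the dispensed dose is not defined. If it were rounded to the nearest prefilled size in 15.22 (an assumption), the dividing line between 5,000 and 7,500 IU is 6,250 IU, or 62.5 kg. A 60 kg patient would then stay at 5,000 IU, and the increase would begin at 63 kg. The footnote to 7.1 on wasting part of a syringe points instead to the exact amount. On that reading a 40 kg patient in months 2-6 receives 6,000 IU, and 5,000 IU is a cut of 1 − 5,000/6,000 = 17%.

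**5. Share of patients on each side.** The documents give no weight distribution. Assume a normal distribution with mean 60-85 kg and SD 12-20 kg, with weights rounded to whole kilograms. The share above 50 kg is 1 − Φ((50.5 − mean)/SD). This runs from 68% (mean 60, SD 20) to 99.8% (mean 85, SD 12). The share at 40 kg or less is Φ((40.5 − mean)/SD), from 16% down to 0.01% for the same two cases.

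**6. Post-procedure overlap.** At 40 kg or less in months 2-6, the optional 5,000 IU allowed from 24 hours equals the therapeutic table dose withheld until 72 hours. Apixaban has a similar overlap. A patient on a strong CYP3A4 inhibitor is already at 2.5 mg twice daily (8.1, 9.1), which is also the platelet-reduced dose and the post-procedure prophylactic dose.

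**The case against.** The strongest reply is that a dose of 5,000 IU cannot be reduced to 7,500 IU. The verb shows that 8.2(2) has the full dose in mind, and step 3 confirms that the rule works there. This stands as evidence of intent. It does not give an instruction for a patient already lowered: 8.2(2) states a target, not a ceiling. The renal rule in 8.1, by contrast, names both starting and ending doses.

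Three stronger readings are tempting, and the documents do not support them.

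- **That the rules bias the primary comparison towards apixaban.** The pre-procedure increase can arise only on dalteparin, because apixaban is simply stopped before a procedure. But the label overlap exists in both arms. The increase also concerns one dose per procedure, still below the full table dose, with none on the procedure day. Nothing in the documents gives the frequency of procedures in such patients or the bleeding risk per dose. The thrombocytopenia figure of about 11% in 15.28 carries no platelet threshold, so a count built on it would rest on invented fractions.
- **That 5,000 IU is never a cut at 40 kg or less.** In month 1 it is a 33% cut. In months 2-6 the zero holds for the table dose, subject to the wasting instruction.
- **That a renal-reduced patient already at 100 IU/kg simply gets no pre-procedure cut.** That dose applies only after month 1. Elsewhere 8.1 requires patients with clearance of 30 ml/min or less to discontinue, so whether anyone remains on it is itself contradictory.

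**Conclusion.** The conflict is real but narrow. Above 50 kg, for a dalteparin patient with platelets of 25,000-50,000 who needs a procedure, the 8.2(2) dose as written exceeds the dose that 8.1 has put in force, by 20% at 60 kg and 80% at 90 kg. This assumes that the exact 100 IU/kg is given. That most patients weigh more than 50 kg rests on assumed weights, but it held across the range tried. At 40 kg or less, in months 2-6 only, the platelet step does not change the table dose, and the prophylactic and therapeutic labels name the same dose.

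The number affected cannot be derived. It is probably small, since platelet band, procedure and weight must coincide. This is a point of patient safety and uniform conduct. It is not evidence of a distorted primary comparison, and it leaves sample size, alpha and power untouched.

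**What to change.** The sponsor's clinical team should reconcile 8.1, 8.2 and table 7.11 and state:

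- how the pre-procedure step applies to a patient already on a dose lowered under 8.1, and how 100 IU/kg is turned into a dispensed dose;
- what the platelet step and the post-procedure step mean where the table dose is already 5,000 IU, with the matching clarification for apixaban patients already at 2.5 mg twice daily;
- how the renal-reduced case fits with the rule in 8.1 that clearance of 30 ml/min or less means discontinuation.

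The choice of doses belongs to the clinical team, and none is proposed here. The cost is a few sentences in an amendment and a memo to sites, with no extra visits, data or patients.

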10.0 Adverse Event (AE) Reporting and Monitoring

10.1 Adverse Event Characteristics

An Adverse Event [AE] is defined as any new untoward medical occurrence or worsening of a preexisting medical condition in a patient or clinical investigation subject administered an investigational (medicinal) product and that does not necessarily have a causal relationship with this treatment. An AE can therefore be any unfavorable and unintended sign (including an abnormal laboratory finding, for example), symptom, or disease temporally associated with the use of investigational product, whether or not considered related to the investigational product.

CTCAE term (AE description) and grade: The descriptions and grading scales found in the revised NCI Common Terminology Criteria for Adverse Events (CTCAE) version 4.0 will be utilized for AE reporting. All appropriate treatment areas should have access to a copy of the CTCAE version 4.0. A copy of the CTCAE version 4.0 can be downloaded from the CTEP web site:

(http://ctep.cancer.gov/protocolDevelopment/electronic_applications/ctc.htm)

10.11 Adverse event monitoring and reporting is a routine part of every clinical trial. First, identify and grade the severity of the event using the CTCAE version 4.0. Next, determine whether the event is expected or unexpected (see Section 10.2) and if the adverse event is related to the medical treatment or procedure (see Section 10.3). With this information, determine whether the event must be reported as an expedited report (see Section 10.4). **Important:** Expedited adverse event reporting requires submission of a Med Watch report(s). Expedited reports are to be completed within the timeframes and via the mechanisms specified in Sections 10.4. All AEs reported via expedited mechanisms must also be reported via the routine data reporting mechanisms defined by the protocol (see Sections 10.5 and 18.0).

10.12 Each CTCAE term in the current version is a unique representation of a specific event used for medical documentation and scientific analysis and is a single MedDRA Lowest Level Term (LLT).

- **NOTE:** A severe AE, as defined by the above grading scale, is **NOT** the same as serious AE which is defined in the table in Section 10.4.

10.2 Expected vs. Unexpected Events

- The determination of whether an AE is expected is based on agent-specific information provided in Section 15.0 of the protocol.

- Unexpected AEs are those not listed in the agent-specific information provided in Section 15.0 of the protocol.

NOTE: “Unexpected adverse experiences” means any adverse experience that is neither identified in nature, severity, or frequency of risk in the information provided for IRB review nor mentioned in the consent form.

10.3 Assessment of Attribution

When assessing whether an adverse event is related to a medical treatment or procedure, the following attribution categories are utilized:

Definite - The adverse event *is clearly related* to the agent(s).

Probable - The adverse event *is likely related* to the agent(s).

Possible - The adverse event *may be related* to the agent(s).

Unlikely - The adverse event *is doubtfully related* to the agent(s).

Unrelated - The adverse event *is clearly NOT related* to the agent(s).

Events determined to be possibly, probably or definitely attributed to a medical treatment suggest there is evidence to indicate a causal relationship between the drug and the adverse event.

10.31 Special Situations for Expedited Reporting

10.311 Persistent or Significant Disabilities/Incapacities

Any AE that results in persistent or significant incapacity or substantial disruption of the ability to conduct normal life functions (formerly referred to as disabilities), congenital abnormalities or birth defects, must be reported immediately if they occur at any time following treatment with an agent under an IND/IDE since they are considered to be a serious AE and must be reported to the sponsor as specified in 21 CFR 312.64(b).

10.312 Death

- Any death occurring within 30 days of the last dose, regardless of attribution to an agent/intervention under an IND/IDE requires expedited reporting within 24-hours.
- Any death occurring greater than 30 days with an attribution of possible, probable, or definite to an agent/intervention under an NCI IND/IDE requires expedited reporting within 24-hours.
- **Reportable categories of Death**
 - Death attributable to a CTCAE term.
 - Death Neonatal: A disorder characterized by cessation of life during the first 28 days of life.

- Death NOS: A cessation of life that cannot be attributed to a CTCAE term associated with Grade 5.
- Sudden death NOS: A sudden (defined as instant or within one hour of the onset of symptoms) or an unobserved cessation of life that cannot be attributed to a CTCAE term associated with Grade 5.
- Death due to progressive disease should be reported as **Grade 5 “Neoplasms benign, malignant and unspecified (incl cysts and polyps) – Other (Progressive Disease)”** under the system organ class (SOC) of the same name. Evidence that the death was a manifestation of underlying disease (e.g., radiological changes suggesting tumor growth or progression: clinical deterioration associated with a disease process) should be submitted.

10.313 Secondary Malignancy

- A *secondary malignancy* is a cancer caused by treatment for a previous malignancy (e.g., treatment with investigational agent/intervention, radiation or chemotherapy). A secondary malignancy is not considered a metastasis of the initial neoplasm.
- All secondary malignancies that occur following treatment with an agent under an IND/IDE to be reported. Three options are available to describe the event:
 - Leukemia secondary to oncology chemotherapy (e.g., Acute Myelocytic Leukemia [AML])
 - Myelodysplastic syndrome (MDS)
 - Treatment-related secondary malignancy
- Any malignancy possibly related to cancer treatment (including AML/MDS) should also be reported via the routine reporting mechanisms outlined in each protocol.

10.314 Second Malignancy

- A second malignancy is one unrelated to the treatment of a prior malignancy (and is NOT a metastasis from the initial malignancy). Second malignancies require ONLY routine reporting.

10.315 Pregnancy

If, following initiation of the investigational product, it is subsequently discovered that a study subject is pregnant or may have been pregnant at

the time of investigational product exposure, including during at least 5 half-lives after product administration, the investigational product will be permanently discontinued in an appropriate manner (eg, dose tapering if necessary for subject safety).

The site investigator must immediately notify ACCRU of this event via the Pregnancy Surveillance Form within 24 hours and in accordance with SAE reporting procedures.

Follow-up information regarding the course of the pregnancy, including perinatal and neonatal outcome and, where applicable, offspring information must be reported on a Pregnancy Surveillance Form.

Any pregnancy that occurs in a female partner of a male study participant should be reported to BMS. Information on this pregnancy may also be collected on the Pregnancy Surveillance Form.

Protocol-required procedures for study discontinuation and follow-up must be performed on the subject unless contraindicated by pregnancy (eg, x-ray studies). Other appropriate pregnancy follow-up procedures should be considered if indicated.

10.316 Overdose

An overdose is defined as the accidental or intentional administration of any dose of a product that is considered both excessive and medically important. All occurrences of overdose must be reported as SAEs.

10.317 Drug Induced Liver Injury (DILI)

Wherever possible, timely confirmation of initial liver-related laboratory abnormalities should occur prior to the reporting of a potential DILI event. All occurrences of potential DILIs, meeting the defined criteria, must be reported as SAEs.

Potential drug induced liver injury is defined as

1. AT (ALT or AST) elevation > 3 times upper limit of normal (ULN)
AND

2. Total bilirubin > 2 times ULN, without initial findings of cholestasis (elevated serum alkaline phosphatase),
AND

AND

3. No other immediately apparent possible causes of AT elevation and hyperbilirubinemia, including, but not limited to, viral hepatitis, pre-existing chronic or acute liver disease, or the administration of other drug(s) known to be hepatotoxic.

10.318 Other Safety Considerations

Any significant worsening noted during interim or final physical examinations, electrocardiograms, x rays, and any other potential safety assessments, whether or not these procedures are required by the protocol, should also be recorded as a nonserious or serious adverse event, as appropriate, and reported accordingly.

10.4 Expedited Reporting Requirements for Studies using Commercial Agent(s) ONLY:**Expedited Reporting Requirements for Adverse Events that Occur in a Non-IND/IDE trial within 30 Days of the Last Administration of a Commercial Agent^{1,2}**

FDA REPORTING REQUIREMENTS FOR SERIOUS ADVERSE EVENTS (21 CFR Part 312) NOTE: Investigators MUST immediately report to ACCRU ANY Serious Adverse Events, whether or not they are considered related to the investigational agent(s)/intervention (21 CFR 312.64) An adverse event is considered serious if it results in ANY of the following outcomes:
 
 1) Death 2) A life-threatening adverse event 3) An adverse event that results in inpatient hospitalization or prolongation of existing hospitalization for \geq 24 hours 4) A persistent or significant incapacity or substantial disruption of the ability to conduct normal life functions 5) A congenital anomaly/birth defect. 6) Important Medical Events (IME) that may not result in death, be life threatening, or require hospitalization may be considered serious when, based upon medical judgment, they may jeopardize the patient or subject and may require medical or surgical intervention to prevent one of the outcomes listed in this definition. (FDA, 21 CFR 312.32; ICH E2A and ICH E6). 				

ALL SERIOUS adverse events that meet the above criteria MUST be immediately reported to ACCRU within the timeframes detailed in the table below.
				
Hospitalization	Grade 1 Timeframes	Grade 2 Timeframes	Grade 3 Timeframes	Grade 4 & 5 Timeframes
Resulting in Hospitalization \geq 24 hrs	1 Business Day			24-hour 1 Business Day
Not resulting in Hospitalization \geq 24 hrs	Not required		1 Business Day	

Expedited AE reporting timelines are defined as:
 
 o "24-Hour; 1 Business Day" - The AE must initially be reported via MedWatch within 24 hours of learning of the AE, followed by a complete expedited report within 1 business day of the initial 24-hour report. o "1 Business Day" - A complete expedited report on the AE must be submitted within 1 business day of learning of the AE. 				

¹Serious adverse events that occur more than 30 days after the last administration of investigational agent/intervention and have an attribution of possible, probable, or definite require reporting as follows: Expedited 24-hour notification followed by complete report within 1 business day for:
 
 • All Grade 4, and Grade 5 AEs 
Expedited 1 business day reports for:
 
 • Grade 2 adverse events resulting in hospitalization or prolongation of hospitalization • Grade 3 adverse events 
² For studies using PET or SPECT IND agents, the AE reporting period is limited to 10 radioactive half-lives, rounded UP to the nearest whole day, after the agent/intervention was last administered. Footnote "1" above applies after this reporting period.
				
Effective Date: May 5, 2011				

Additional Instructions:

1. An increased incidence of an expected adverse event (AE) is based on the patients treated for this study at their site. A list of known/expected AEs is reported in the package insert or the literature, including AEs resulting from a drug overdose.

2. Follow site-specific reporting guidelines.
3. Submit MedWatch form 3500A to the ACCRU SAE Coordinator via fax [REDACTED]. The ACCRU SAE Coordinator will forward the report to Bristol-Myers Squibb via E-mail within 1 business day to [REDACTED] or [REDACTED] and will also forward to Pfizer via [REDACTED].
4. The ACCRU SAE Coordinator will forward to [REDACTED] as appropriate. The ACCRU IND Coordinator will assist the sponsor-investigator in notifying the FDA if required.

EVENT TYPE	REPORTING PROCEDURE
Other Grade 4 or 5 Events and/or Any Hospitalizations During Treatment Not Otherwise Warranting an Expedited Report	Notification form: Grade 4 or 5 Non-AER Reportable Events/ Hospitalization Form to ACCRU within 5 working days ¹

1. If FDA Form 3500A (MedWatch) was completed, this form need not be completed.

